Describe the purpose for the proposed project.

We are building on previous work to identify opportunities to meet the needs of perinatal fathers. The term perinatal encompasses the time leading up to and immediately following the birth of a child. Father involvement in child rearing is beneficial to mothers and children, but fathers are routinely overlooked by available support opportunities at the transition to parenthood. Our pilot project seeks to apply research evidence and best practices to address the disparity in socioemotional community support and education programs serving perinatal fathers. In a previous pilot study, we learned from fathers participating in focus groups that they are interested in opportunities to connect with other fathers in the same life stage to talk about their experiences and learn from each other. We also learned that fathers worry about meeting varied role expectations, that available resources tend to overlook the unique experiences of fathers, and that it can be challenging to find quality information in a digital world saturated with conflicting information about parenting. This project seeks to address these primary issues through community-based, father-centric support and educational programs. WCNC education staff will facilitate a discussion-based group mentoring program for fathers who are expecting or recently had a baby. This program seeks to increase connection with other fathers, reduce stress related to parenting a baby, and increase parenting confidence. We plan to evaluate the feasibility of the program through satisfaction surveys and other measures of the program's implementation. We also plan to evaluate the effectiveness of the program by providing participants with surveys asking about their well-being, knowledge, confidence in parenting, and their satisfaction with their social networks. We are additionally developing educational podcasts focused on topics relevant to prenatal and postpartum fathers, which will be evaluated as a supplementary component to the mentoring program. Our research objectives are the following: Study 1 Objective 1 (Primary): We seek to determine the feasibility and acceptability of a program targeting perinatal fathers offered in a community clinic setting. Study 1 Objective 2 (Primary): Examine whether participating in a discussion-based group mentoring program increases the likelihood of positive short-term outcomes for fathers. Study 1 Objective 3 (Secondary): Identify whether listening to brief, targeted educational podcasts predicts increased positive outcomes for fathers over and above the mentoring group alone. Study 2 Objective 1 (Primary): Identify whether participants who listen to brief,

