Participants from the mentoring group or who are on a waiting list for the next mentoring group will be invited to complete electronic surveys at four time points over four months, with four weeks between each survey. A WCNC staff member ([name]) will send out a survey link to consented participants at each time point. Surveys will be available through [name]'s CSU Qualtrics account. Participants will enter their unique ID number in each survey so surveys can be linked over time. Surveys will assess demographics and outcomes of interest, including stress, mental health symptoms, parenting knowledge, confidence in parenting, the coparenting relationship, and satisfaction with their social networks. Participants will also be asked about whether or not they listened to podcasts.

Who will conduct this procedure?

Personnel

[name]

Personnel
[name]

External User

Indicate the frequency and duration of visits/sessions as well as the subject's total time commitment for the study.

15-30 minutes for each electronic outcome survey over 4 surveys. Total time: 1-2 hours.

Describe how the data will be collected (i.e. in person or online).

Online through Qualtrics

Will any video, photography, or audio be recorded as part of this procedure?

No

Will data be collected anonymously?

No

Procedure Description
Mentoring Program Satisfaction Surveys

This procedure is:

Research Activity Involving Participants, Participants Data, or Biospecimens

This procedure is:

Experimental

Where and when will this procedure take place?

Participants who have attended the mentoring program will be invited to complete an electronic satisfaction survey through [name]'s CSU Qualtrics account following completion of the group program. Surveys will ask about demographics, what participants liked or didn't like about the program, their perceptions of the group environment, and supportive group dynamics. Participants will also be given a brief (1-2 minute) electronic questionnaire at the beginning of each week of the program assessing their engagement in homework. Survey links will be sent by a member of the WCNC staff ([name]) to maintain separation of participant contact information from data. [name] will manage the data on the research side.

Who will conduct this procedure?

Personnel

[name]

Personnel

[name]

External User

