Any contact with participants to provide referrals will be noted and tracked by the staff member.

Will any video, photography, or audio be recorded as part of this procedure?

No

Will data be collected anonymously?

No

Privacy and Confidentiality

Explain how the established data management plan along with consent processes and other elements of the research design address the following.

Privacy is considered from the perspective of the participant and is a right to be protected. Privacy refers to an individual's interest in controlling others' access to themselves.

Based on their privacy interests, participants may want to control:

- The time and place where they give information
- The nature of the information they give
- Who receives and can use the information

For example, persons might not want to be seen entering a place that might stigmatize them, such as a pregnancy-counseling center identified as such by signs on the front of the building.

Describe how you will protect subject's privacy.

Participants will be able to complete electronic surveys in locations they are comfortable with, as chosen by the participant. Participants who attend the small-group mentoring program will be associating with a business they have already chosen to be affiliated with prior to being recruited for the study. If a participant is not comfortable attending the program due to its location or the other group participants, they may choose to stop attending the mentoring program at any time. Participants who complete the podcast survey will be able to provide their responses anonymously.

Confidentiality is about data. Confidentiality pertains to protecting information from disclosure based on an agreement between the participant and the researcher. When an individual shares information in a relationship of trust and expects it to be kept private or will be disclosed only with specific permissions, researchers must uphold this agreement and maintain data appropriately.

Describe how you will maintain the confidentiality of subjects' information.

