Statistical Design and Power

Study Title: DadSpace: Increasing Community Support Resources for Perinatal Fathers

Study ID: 1754

Date of Plan: 6/14/2021

Statistical Design and Power

We anticipate that by the conclusion of the DadSpace program feasibility trial, 28 fathers will have completed the program as well as pretests and posttests, and 28 fathers will have completed pre- and posttests as wait-list controls. With a moderate effect size of Cohen's $d = .50$, this sample size will provide power = .95 using a 2 (time) by 2 (group) repeated measures ANOVA with stability coefficients of $r = .50$. Power will be lower but still sufficient (.81) to detect a small/moderate effect size of $d = .33$. Given that pilot trials of DadSpace (e.g., *Becoming Fathers*) and focus groups have indicated that DadSpace is likely to be effective, we believe that effect sizes of .40-.50 are likely on each of the primary outcome measures.

In section 4.2, we entered multiple "additional measures," all of which assess program implementation. These measures provide us with feedback as to how the DadSpace program was delivered and received by the participants. Following best practices (e.g., Berkel et al., 2011), this information will serve two purposes: to provide guidance on strengthening the DadSpace program, and to assess how variations in implementation are related to degree of program impact. In order to assess the latter, exploratory correlational analyses will be conducted between implementation variables and gain scores on the pre-/posttest measures of program impact.

<https://doi.org/10.1007/s11121-010-0186-1>

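### The single satisfaction survey goes out only after the group program ends, so the acceptability result in primary Objective 1 is likely to over-represent fathers who stayed

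*Protocol*

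**What the plan says.** Study 1 Objective 1, marked as primary in the protocol's statement of purpose, reads: "We seek to determine the feasibility and acceptability of a program targeting perinatal fathers offered in a community clinic setting". The same section gives the means: "We plan to evaluate the feasibility of the program through satisfaction surveys and other measures of the program's implementation".

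Under Procedures, Mentoring Program Satisfaction Surveys, the invitation is: "Participants who have attended the mentoring program will be invited to complete an electronic satisfaction survey". The timing is "following completion of the group program". The survey asks what fathers liked and disliked, and about the group environment and its dynamics. The same entry adds a short weekly questionnaire, which covers homework engagement only.

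Early leaving is foreseen. Under Privacy and Confidentiality, fathers uncomfortable with the location or the other members are told "they may choose to stop attending the mentoring program at any time". Risks and Benefits likewise lets a father who is not comfortable sharing withdraw from the group.

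Facilitators record attendance and rate engagement (Procedures, Participation in the Mentoring Program). The SAP says its implementation measures show how the program was delivered and received. It will use them to strengthen the program and, in exploratory analyses, correlate them with pre/post gain scores. Neither document defines what counts as having attended, describes a contact when a father stops, or gives a denominator or a non-response rule for acceptability.

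**The concern.** The fathers whose views bear most on acceptability are those who tried the program and stopped. The reasons for stopping that the protocol foresees (the setting, the other members, discomfort with sharing) are themselves acceptability problems. Under the present timing these fathers are asked after a gap, and it is reasonable to expect fewer of them to reply than of fathers who have just finished.

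If leavers are less satisfied and reply less often, the satisfaction figure for a primary objective is biased upward. The trial would also learn little about why fathers left, which is among the most useful things a feasibility study can bring to the next version of a program.

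**Working it through.** **1. How many satisfaction contacts are planned?** Two stated figures can be reproduced.

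- Time commitment: one satisfaction survey of 10-20 minutes plus eight weekly homework surveys of 1-2 minutes each. Low end 10 + 8×1 = 18; high end 20 + 8×2 = 36. This matches the stated 18-36 minutes.
- Payment: 8 + 10 + 10 + 10 + 6 = $44, the stated total, with a single $6 satisfaction payment.

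Both agree with one satisfaction contact per father and none added at early exit.

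**2. How late is that contact for a leaver?** There are 8 sessions. Taking them as weekly, as the weekly homework questionnaire implies, a father who stops after session 2 is asked about 8 − 2 = 6 weeks later.

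**3. Does anything else collect the missing information?**

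| Source | Covers early leavers? | Shows what he disliked or why he left? |
|---|---|---|
| Weekly questionnaire | Not stated | No, homework only |
| Four outcome surveys | No rule ends them when a father stops | Not among the listed topics (stress, mental health, parenting, coparenting, social networks, podcast listening) |
| Attendance, facilitator-rated engagement | Yes | No, shows only that he stopped or was less engaged |
| Satisfaction survey | Yes, but late | Asks about likes and dislikes |

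**4. Possible size.** The documents give no dropout, response or satisfaction rate, so every rate here is an assumption. Let a be the share who leave and do not answer, S the satisfaction of stayers (all assumed to answer) and L that of leavers.

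- Satisfaction among all starters = (1 − a)×S + a×L
- Overstatement = S − that value = a×(S − L)

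With S = 90%:

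| a | L = 70% | L = 50% | L = 30% |
|---|---|---|---|
| 0% | 0 points | 0 points | 0 points |
| 10% | 2 | 4 | 6 |
| 20% | 4 | 8 | 12 |
| 30% | 6 | 12 | 18 |
| 40% | 8 | 16 | 24 |

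For example, a = 20% and L = 50% give 0.8×0.90 + 0.2×0.50 = 82%, while the survey shows 90%. With no assumption about L, a = 20% bounds the value between 0.8×0.90 = 72% and 72% + 20% = 92%.

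**5. At a realistic sample size.** Suppose 28 fathers start (a number borrowed from the SAP for scale only), 22 stay with 20 satisfied, and 6 leave with 2 satisfied. Exact binomial 95% intervals:

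- Stayers only: 20/22 = 91% (71-99%)
- All starters: 22/28 = 79% (59-92%)
- Leavers silent and counted as not satisfied: 20/28 = 71% (51-87%)

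**The case against.** The strongest reply is that the plan already invites leavers. The invitation sets no minimum number of sessions and no completion condition; on its plain wording the phrase about program completion fixes when the survey goes out, not who receives it. A father who came twice has attended. That stands. A reader might infer that leavers are dropped however the text is read, but the documents do not support this: they are reached late, and late non-response is a risk rather than an exclusion.

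A reader might also infer that the SAP restricts acceptability to completers, because it expects that "28 fathers will have completed the program as well as pretests and posttests". That sentence projects the sample for the power calculation of the repeated measures ANOVA. It is not an acceptability denominator, and the SAP states none.

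Three further points have weight. Contact with leavers may continue through the four outcome surveys, and the $6 payment has no stated attendance condition, so their response could be better than feared. Attendance and engagement records mean dropout will be visible beside any satisfaction rating. And no acceptability threshold is stated, so no documented decision is shown to change; the intervals in the 28-father example overlap widely.

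None of this supplies a leaver's reasons or a denominator. The survey measures attachment, and the section 4.2 list of additional measures to which the SAP refers, are not in the text available here. An exit item there cannot be ruled out, but the procedures describe none.

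**Conclusion.** The point holds as one of timing and reporting. The plan has one mentoring-program satisfaction survey, sent after the program ends; nothing else described asks a leaver what he disliked or why he stopped; and acceptability has no stated denominator. Followed as written, the plan will probably give an acceptability result that leans toward stayers.

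The upward direction assumes that leavers are less satisfied and reply less often than stayers. That is plausible, but it is not documented, and the present design is poorly placed to test it. The amount cannot be computed. Under the assumed rates above it runs from 2 to 24 points when 10-40% leave and do not answer, and it is zero with no dropout. The trial itself remains valid; what is at risk is the reading of one part of a primary objective. The change is worth making because it is cheap and because reasons for leaving are harder to recover once a group has ended.

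**What to change.** In the Mentoring Program Satisfaction Surveys entry, in both copies of the protocol form:

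- Define attendance for this purpose as at least one session, and send the existing survey link to every consented father who meets it.
- Send it at program end or, if earlier, once the facilitator's weekly attendance record shows that he has stopped. Define in advance what counts as stopped, as a number of missed sessions.

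In the SAP, add that satisfaction will be reported over all fathers who started, with the response rate and the number of sessions attended, plus a bound that counts non-responders as not satisfied.

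The parts are already in place: facilitators keep attendance, a clinic staff member sends the links, and the survey and its $6 payment are planned. The trigger can stay inside the clinic, so identities remain separate from survey data. The costs are a small protocol amendment with ethics review, a weekly handover of attendance to the person sending links, and some ratings based on partial exposure to the program. Reporting by sessions attended keeps those ratings identifiable.

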Paternal mental health over the transition to parenthood is an additional concern affecting family well-being (Paulson et al., 2016). Fathers in the U.S. have been found to experience perinatal depression at a rate of about 13% (Cameron, Sedhov, & Tomfohr-Madsen, 2016), and depressive symptoms have been found to increase over the first 5 years of the child's life by an average of 68% (Garfield et al., 2014). Depressive symptoms place men at an increased risk of suicide, and suicide rates for men in Colorado are rising (Colorado Department of Public Health and Environment, 2018), suggesting needs are not being met. Parent depression is also related to later interparental conflict, which has negative effects on children (Shelton & Harold, 2008). Paternal perinatal depression is frequently overlooked, and there has been a recent call for perinatal and pediatric health professionals to screen for depressive symptoms in fathers and provide resource referrals ([name], 2020; Walsch et al., 2020). Available services have not yet caught up to this need. In Larimer County, a Department of Health and Environment coalition on postpartum depression, anxiety, and mood disorders focuses only on maternal mental health (LCDHE, n.d.). This project is grounded in bioecological theory, which proposes that development occurs through a process of interactions between individual characteristics and social contexts such as relationships, institutions, and policies across time (Bronfenbrenner & Morris, 2006). Since perinatal fathers are adjusting to fatherhood within families and communities, we seek to utilize the clinical, media, and social spaces perinatal fathers interact with to engage fathers in educational resources and intervention programs targeted to their needs.

Please describe the expertise you have, or have access to, which prepares you to conduct research in this location and/or with this subject population, including specific qualifications (e.g., relevant coursework, background, experience, and training).

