Identifiable information will only be accessible to WCNC staff. WCNC staff will provide ID numbers to each participant to use for completing their surveys. Research staff will only have access to participant ID numbers paired with survey data, not participant names or contact information. Survey responses will be aggregated for the purposes of reporting to community partners, stakeholders, publications, and grant reports. Given the small sample size, it is possible a person's data could be linked to their demographic information. To mitigate this risk, any data reported by demographic will be withheld if the demographic subgrouping contains a population of 3 or fewer people.

Clinical Trial

Will participants will be prospectively assigned to one or more interventions (including placebo or other control)?

Yes

Will the study evaluate the effects of the intervention on health-related outcomes (biomedical or behavioral)?

Yes

Does this study involve an FDA-regulated drug or device?

No

Will the study be conducted as a
Single-Site Clinical Trial

Will this study be posted on ClinicalTrials.gov?

Yes

ClinicalTrials.gov Registration# (or pending)

Pending

Additional information and support available through CSU Quality Assurance:

[contact]

Participant Population

Are you interacting or intervening with participants?

Yes

Provide an estimate of the anticipated participant total.

56

Are you analyzing existing data records or biospecimens?

No

Inclusion and Exclusion Criteria (e.g., Participants must have 20/20 vision, Participants must be 30-45 years of age, etc.) This should match your screening, consent, and recruitment materials.

Please list all inclusion criteria

Participants must be expecting a baby or have a baby less than one year of age and have signed up to participate in the DadSpace mentoring program at WCNC

Please list all exclusion criteria

Less than 18 years of age, non-English-speaking.

What is the rationale for studying the requested group(s) of participants?

These participants comprise the target population of people served by the clinic and the primary focus of the intervention.

Will you use a screening procedure, instruments, tools, questionnaires etc.?

Yes

Describe any planned screening procedures. Attach your screening document(s) (e.g., health history questionnaire), if applicable at the end of the form.

Participants will be screened for inclusion and exclusion criteria as listed above. Screening questions are attached.

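### The effect test has no term for perinatal stage, although expecting and postpartum fathers are pooled and no balancing of the arms on stage is described

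*Protocol*

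**What the plan says.** **Who is eligible.** Protocol, Participant Population, inclusion criteria: "Participants must be expecting a baby or have a baby less than one year of age", together with sign-up for the program at the clinic. No cap, quota or stratum by stage is given.

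**How the arms arise.** Protocol, Procedures, Online Surveys: "Participants from the mentoring group or who are on a waiting list for the next mentoring group will be invited to complete electronic surveys". Surveys are sent four times, four weeks apart. The Clinical Trial section answers yes to prospective assignment to interventions, but no section says how fathers come to be in the current group or on the list. New groups start monthly and the program has eight sessions (Participation in the Mentoring Program).

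**What is measured.** Stress, mental health symptoms, parenting knowledge, parenting confidence, coparenting and satisfaction with social networks (Online Surveys).

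**How the effect is tested.** SAP, Statistical Design and Power: the sample is "28 fathers will have completed the program as well as pretests and posttests" and "28 fathers will have completed pre- and posttests as wait-list controls", compared "using a 2 (time) by 2 (group) repeated measures ANOVA" with a pre/post correlation of .50. Time and group are the only factors. No covariate, stratum or sensitivity analysis for stage, baby's age or a birth during follow-up is named.

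**The concern.** A father who answers the pretest while expecting and the posttest with a newborn at home may change on stress, confidence, knowledge and coparenting for reasons unrelated to the program. The time-by-group term cannot separate that change from the program's effect unless such births are equally common in the two arms. Nothing in the plan secures this, and the model has no term that would correct for a difference.

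At stake is the reading of Study 1 Objective 2, one of the two primary objectives of that study. The direction is not known in advance. A newborn may raise stress and hide a benefit, or it may raise confidence and knowledge through practice and imitate one.

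**Working it through.** **1. The plan's own figure.** The SAP states: "With a moderate effect size of Cohen's $d = .50$, this sample size will provide power = .95". Inputs from the SAP: N = 56, two time points, r = .50. Assumed, because not stated: two-sided alpha .05. With f = d/2 = .25, the noncentrality is f² × N × 2 / (1 − r) = .0625 × 56 × 2 / .5 = 14. On 1 and 54 degrees of freedom the power is .957, so the .95 reproduces. The SAP's second figure, .81 at d = .33, does not: the same formula gives a noncentrality of 6.10 and power .68. That is a separate matter and nothing below depends on it.

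**2. Scale.** With r = .50 the SD of the gain score is √(2 × (1 − .50)) = 1.0 outcome SD. I read the SAP's expected .40 to .50 as a difference between arms in mean gain, in those units.

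**3. Are births between the tests likely?** The SAP does not say which two of the four surveys are pretest and posttest, so I take 8 or 12 weeks. Assume due dates are spread evenly over the remaining 26 or 13 weeks of pregnancy. The share of expecting fathers whose baby arrives between the tests is then:

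| Interval | 26 weeks remaining | 13 weeks remaining |
|---|---|---|
| 8 weeks | 8/26 = 31% | 8/13 = 62% |
| 12 weeks | 12/26 = 46% | 12/13 = 92% |

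**4. Bias formula.** Let δ be the shift in gain caused by a birth, in SD, and let p₁ and p₀ be the shares of program and wait-list fathers with a birth between the tests. The spurious part of the group difference is δ × (p₁ − p₀). It is zero when p₁ = p₀.

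**5. Illustration.** Neither δ nor p₁ − p₀ is in the documents. Take a 20-point difference (50% against 30%) and δ of 0.3, 0.5 or 0.8. The variance of the gain in each arm is 1 + δ² × p(1 − p), and SE = √((v₁ + v₀)/28). The false-positive rate comes from a noncentral t on 54 degrees of freedom.

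| δ (SD) | Bias (SD) | Share of d = .50 | SE | False-positive rate |
|---|---|---|---|---|
| 0.3 | 0.06 | 12% | .270 | .055 |
| 0.5 | 0.10 | 20% | .275 | .065 |
| 0.8 | 0.16 | 32% | .286 | .085 |

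Against d = .40 the shares are 15%, 25% and 40%.

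**6. What a 20-point difference requires.** If it came only from different shares of expecting fathers, those shares would have to differ by 20 points divided by the proportion in step 3: 0.20/0.92 = 22 points at the least and 0.20/0.31 = 65 points at the most. A difference in how close the due dates are could produce it with a smaller gap.

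**7. Equal births.** With 40% in both arms, the bias is zero and the gain variance is 1 + 0.24δ², that is 1.02, 1.06 and 1.15. Power of the gain-score comparison at a between-arm difference of .50 moves from .45 to .44, .43 and .40. This may overstate the loss, because the SAP's r = .50 is meant for this same mixed population and may already include the noise.

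**The case against.** Pooling is deliberate. The program is meant for both kinds of father, this is a pilot, and a concurrent wait-list arm removes whatever is common to both arms. All of that stands, and pooling in itself is not the fault.

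Several stronger readings are tempting, and the documents do not support them.

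- *Any uneven split of births biases the result.* A reader might infer this from 28 fathers per arm. Chance imbalance is ordinary sampling error and is already in the standard error. Simulation with equal birth probability in the two arms leaves the false-positive rate at .05.
- *The bias is large.* A split such as 40% against 10% births would be needed. With 8 of 13 remaining weeks covered, that means 65% expecting in one arm and 16% in the other (.40/.615 and .10/.615). With 8 of 20 weeks it means 100% and 25%. Nothing in the documents suggests this. Sorting by due date could go either way, since a father near his date might join early or put it off, and a wait for the next monthly group leaves limited room for it.
- *The protocol itself shows that symptoms shift at birth.* Its Background says "depressive symptoms have been found to increase over the first 5 years of the child's life by an average of 68" percent. That is a five-year average and says nothing about change at the birth.
- *Stage is not recorded.* The screener must already establish eligibility and the surveys collect demographics, but both instruments are attachments not reproduced in the text. The absence of adjustment is likewise read from a short SAP that names only time and group.

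After these deductions, allocation is still undescribed and no analytic use of stage is stated.

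**Conclusion.** The concern holds in a conditional form. As written, the plan leaves a plausible prognostic variable outside both the formation of the arms and the model. If the arms differ in stage, the time-by-group term mixes the effect of a birth with the effect of the program. If they do not, the cost is a little precision.

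The size cannot be derived from the documents. The range of 0.06 to 0.16 SD rests on an assumed 20-point difference in births and an assumed birth effect of 0.3 to 0.8 SD. It is modest beside the expected .40 to .50, though not negligible. If fathers were in fact randomised, which the text neither says nor excludes, any difference in stage at assignment would be chance. The adjustment would then serve precision only, apart from any unequal loss of fathers later.

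**What to change.** 1. On the existing screener, record the due date, or the birth date if the baby is already born.
2. Replace the unadjusted 2 × 2 model with one that adjusts for two baseline variables: stage at pretest (expecting or postpartum), and whether the due date falls between the scheduled pretest and posttest. Using the due date rather than the actual birth avoids adjusting for an event after assignment. In a repeated measures model both must enter as interactions with time, since main effects alone leave the time-by-group term unadjusted. A regression of the gain on group and the two variables does the same.
3. State which two of the four surveys are pretest and posttest, because the second variable depends on it.
4. Report stage by arm at baseline, and say how fathers are assigned to the current group or the wait list.

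The cost is one date item and two degrees of freedom out of about 54. Due dates predict births imperfectly, so some of the effect would remain.

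I would not require the clinic to fill places within stage. Fathers enrol in a fee-paying class before consent and study participation is optional, so that would change the clinic's enrolment and not only the study. Any result for postpartum fathers alone should be labelled exploratory. At the mix in the team's focus groups (15 of 29 postpartum) it would have about 28 × 15/29 ≈ 14 fathers per arm, with power of about .25 at a between-arm difference of .50, against .45 for the full sample on the same gain-score scale.
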